### Causal relationship of adverse event

The definition of an adverse reaction implies at least a reasonable possibility of a causal relationship between a suspected medicinal product and an adverse event. An adverse reaction, in contrast to an adverse event, is characterized by the fact that a causal relationship between a medicinal product and an occurrence is suspected.

Medical judgment should be used to determine the relationship, considering all relevant factors, including pattern of reaction, temporal relationship, de-challenge or re-challenge, confounding factors such as concomitant medication, concomitant diseases and relevant history.

Arguments that may suggest a **reasonable causal relationship** could be:

- The event is **consistent with the known pharmacology** of the drug
- The event is known to be caused by or **attributed to the drug class**.
- **A plausible time to onset of the event** relative to the time of drug exposure.
- Evidence that the **event is reproducible** when the drug is re-introduced

Proprietary confidential information © 2018 Boehringer Ingelheim International GmbH or one or more of its affiliated companies

- **No medically sound alternative etiologies** that could explain the event (e.g. preexisting or concomitant diseases, or co-medications).
- The event is typically **drug-related and infrequent in the general population** not exposed to drugs (e.g. Stevens-Johnson syndrome).
- An indication of dose-response (i.e. greater effect size if the dose is increased, smaller effect size if dose is diminished).

Arguments that may suggest that there is **no reasonable possibility of a causal relationship** could be:

- No plausible time to onset of the event relative to the time of drug exposure is evident (e.g. pre-treatment cases, diagnosis of cancer or chronic disease within days/weeks of drug administration; an allergic reaction weeks after discontinuation of the drug concerned)
- Continuation of the event despite the withdrawal of the medication, taking into account the pharmacological properties of the compound (e.g. after 5 half-lives). Of note, this criterion may not be applicable to events whose time course is prolonged despite removing the original trigger.
- Additional arguments amongst those stated before, like alternative explanation (e.g. situations where other drugs or underlying diseases appear to provide a more likely explanation for the observed event than the drug concerned).
- Disappearance of the event even though the study drug treatment continues or remains unchanged.

#### Intensity of adverse event

The intensity of the AE should be judged based on the following:

Mild: Awareness of sign(s) or symptom(s) which is/are easily tolerated

Moderate: Enough discomfort to cause interference with usual activity

Severe: Incapacitating or causing inability to work or to perform usual activities

#### Pregnancy:

In rare cases, pregnancy might occur in a study. Once a subject has been enrolled into the study, after having taken Nintedanib for idiopathic pulmonary fibrosis, the investigator must report any drug exposure during pregnancy, which occurred in a female subject or in a partner to a male subject to the Sponsor by means of Part A of the Pregnancy Monitoring Form. The outcome of the pregnancy associated with the drug exposure during pregnancy must be followed up and reported by means of Part B of the Pregnancy Monitoring Form.

In the absence of a reportable AE, only the Pregnancy Monitoring Form must be completed, otherwise the NIS AE form is to be completed and forwarded as well within the respective timelines.

#### Expedited Reporting of AEs and Drug Exposure During Pregnancy

The following must be reported by the investigator on the NIS AE form from signing the informed consent onwards until the end of the study to the [REDACTED] at [REDACTED]

Type of Report	Timeline
All serious ADRs associated with Nintedanib, taken for idiopathic pulmonary fibrosis	immediately within 24 hours
All AEs with fatal outcome in patients exposed to Nintedanib, taken for idiopathic pulmonary fibrosis	immediately within 24 hours
All non-serious ADRs associated with Nintedanib, taken for idiopathic pulmonary fibrosis	7 calendar days
All pregnancy monitoring forms	7 calendar days

The same timelines apply if follow-up information becomes available for the respective events. In specific occasions the Investigator could inform the Sponsor upfront via telephone. This does not replace the requirement to complete and fax the NIS AE form.

Information required

For each reportable adverse event, the investigator should provide the information requested on the appropriate (e)CRF pages and the NIS AE form. The NIS AE form and Pregnancy Monitoring Forms should be submitted to the [REDACTED] at [REDACTED]. [REDACTED] For details regarding Pregnancy Monitoring Forms, please refer to [Section 11.2](#), paragraphs entitled, “Pregnancy” and “Expedited Reporting of AEs and Drug Exposure During Pregnancy.”

Reporting of related Adverse Events associated with any other BI drug

The investigator is encouraged to report all adverse events related to any BI drug other than Nintedanib taken for IPF, according to the local regulatory requirements for spontaneous AE reporting at the investigator’s discretion by using the locally established routes and AE report forms. The term AE includes drug exposure during pregnancy, and, regardless of whether an AE occurred or not, any abuse, off-label use, misuse, medication error, occupational exposure, lack of effect, and unexpected benefit.

### **11.3 REPORTING TO HEALTH AUTHORITIES**

Adverse event reporting to regulatory agencies will be done by the MAH according to local and international regulatory requirements.

## **12. PLANS FOR DISSEMINATING AND COMMUNICATING STUDY RESULTS**

Participating physicians and Boehringer Ingelheim will be informed on the progress and status of the IPF registry on a regular basis. An Annual Report will be issued that contains a section on project management (recruitment status, information on technical and administrative issues) and tabular listings of data. Further, meetings of the National Scientific Committee as well as investigator meetings are planned (preferably in the context of major Pulmonology Meetings).

The rights of the investigator and of the sponsor with regard to publication of the results of this study are described in the investigator contract. As a general rule, no study results should be published prior to finalization of the Study Report.

Following database lock, a final report that summarizes the tables of the analysis and explanatory text will be written by the Data Management. Data management according to our contractual agreement will prepare a final Study Report which will be used as a basis for the final Report that will be written internally. After approval from the members of the National Scientific Committee and the sponsor, a final version will be generated that may be used for regulatory purposes, but also as basis for the publications of the registry. Further, the results from the interim analyses will be available for abstracting/publishing in local or international conferences or scientific meetings.

Every effort will be made, given the collected data, in order to produce scientific publications that will in turn contribute to better care for IPF patients and justify the scientific effort. The publication strategy and the authors' list will be agreed between the [REDACTED] of [REDACTED] and the participating investigators. [REDACTED]

will be the official owner of all collected data and results. Every study publication should be consistent with BI's publication policy and guided by the Recommendations for the Conduct, Reporting, Editing, and Publication of Scholarly Work in Medical Journals of the International Committee of Medical Journals (ICMJE) [\[24\]](#).

This study together with the results will be posted to the internet platform Clinicaltrials.gov (CT.gov), in the EU electronic register of post-authorization studies -ENCEPP ([www.encepp.eu/encepp\\_studies/indexRegister.shtml](http://www.encepp.eu/encepp_studies/indexRegister.shtml)) and in the platform of Non - Interventional Study Registries [Dilon ([www.dilon.sfee.gr](http://www.dilon.sfee.gr))] according to local requirements. This webpage is for the electronic registry and is part of the Hellenic Association of Pharmaceutical Companies (SFEE) website.

## **13.2 UNPUBLISHED REFERENCES**

Not applicable

## **ANNEX 1. LIST OF STAND-ALONE DOCUMENTS**

Not Applicable

## **ANNEX 2. ENCEPP CHECKLIST FOR STUDY PROTOCOLS**

*Note: Page number(s) refer to the first page number of the relevant Section.*

Section 1: Milestones	Yes	No	N/A	Page Number(s)
1.1 Does the protocol specify timelines for				
1.1.1 Start of data collection				21
1.1.2 End of data collection				21
1.1.3 Study progress report(s)				-
1.1.4 Interim progress report(s)				-
1.1.5 Registration in the EU PAS register				-
1.1.6 Final report of study results.				21

Comments:

1.1.3 → Not required according to national requirements for non -interventional studies

1.1.4 → Not required as no interim analysis of data is scheduled

1.1.5 → Not required as this study is not considered PASS

Section 2: Research question	Yes	No	N/A	Page Number(s)

Proprietary confidential information © 2018 Boehringer Ingelheim International GmbH or one or more of its affiliated companies

2.1 Does the formulation of the research question and objectives clearly explain:					
2.1.1 Why the study is conducted? (e.g. to address an important public health concern, a risk identified in the risk management plan, an emerging safety issue)				22	& 25
2.1.2 The objective(s) of the study?				26	
2.1.3 The target population? (i.e. population or subgroup to whom the study results are intended to be generalised)				28	
2.1.4 Which formal hypothesis(-es) is (are) to be tested?				-	
2.1.5 If applicable, that there is no a priori hypothesis?				-	

Comments:

2.1.4 & 2.1.5 → This study is not intended for hypothesis testing and will mainly use descriptive statistical methods. Any performed analysis will be of investigational nature.

Section 3: Study design	Yes	No	N/A	Page Number(s)
3.1 Is the study design described? (e.g. cohort, case-control, randomised controlled trial, new or alternative design)				27
3.2 Does the protocol specify the primary and secondary (if applicable) endpoint(s) to be investigated?				
3.3 Does the protocol describe the measure(s) of effect? (e.g. relative risk, odds ratio, deaths per 1000 person-years, absolute risk, excess risk, incidence rate ratio, hazard ratio, number needed to harm (NNH) per year)				

Comments:

3.2 & 3.3 → As explained in section 2 no hypothesis testing is going to be performed therefore no specific effects or endpoints are defined.

Section 4: Source and study populations	Yes	No	N/A	Page Number(s)
4.1 Is the source population described?				28
4.2 Is the planned study population defined in terms of:				
4.2.1 Study time period?				28
4.2.2 Age and sex?				28
4.2.3 Country of origin?				28
4.2.4 Disease/indication?				28
4.2.5 Co-morbidity?				-
4.2.6 Seasonality?				
4.3 Does the protocol define how the study population will be sampled from the source population? (e.g. event or inclusion/exclusion criteria)				28

Comments:

4.2.6 → Seasonal fluctuation and form is not applicable in this study and does not apply to the population of the study and the disease under investigation.

Section 5: Exposure definition and measurement	Yes	No	N/A	Page Number(s)

Section 5: Exposure definition and measurement	Yes	No	N/A	Page Number(s)
5.1 Does the protocol describe how exposure is defined and measured? (e.g. operational details for defining and categorising exposure)				
5.2 Does the protocol discuss the validity of exposure measurement? (e.g. precision, accuracy, prospective ascertainment, exposure information recorded before the outcome occurred, use of validation sub-study)				
5.3 Is exposure classified according to time windows? (e.g. current user, former user, non-use)				
5.4 Is exposure classified based on biological mechanism of action and taking into account the pharmacokinetics and pharmacodynamics of the drug?				
5.5 Does the protocol specify whether a dose-dependent or duration-dependent response is measured?				

Comments:

5.1, 5.2, 5.3, 5.4 & 5.5 → This study is a descriptive epidemiological Study that does not investigate the effect of specific exposure in order to test a hypothesis.

Section 6: Endpoint definition and measurement	Yes	No	N/A	Page Number(s)
6.1 Does the protocol describe how the endpoints are defined and measured?				
6.2 Does the protocol discuss the validity of endpoint measurement? (e.g. precision, accuracy, sensitivity, specificity, positive predictive value, prospective or retrospective ascertainment, use of validation sub-study)				

Comments:

N/A

Section 7: Confounders and effect modifiers	Yes	No	N/A	Page Number(s)
7.1 Does the protocol address known confounders? (e.g. collection of data on known confounders, methods of controlling for known confounders)				
7.2 Does the protocol address known effect modifiers? (e.g. collection of data on known effect modifiers, anticipated direction of effect)				

Comments:

7.1 & 7.2 → No confounders or effect modifiers are discussed since no hypothesis testing or assessment of effects is being performed.

Section 8: Data sources	Yes	No	N/A	Page Number(s)
8.1 Does the protocol describe the data source(s) used in the study for the ascertainment of:				
8.1.1 Exposure? (e.g. pharmacy dispensing, general practice prescribing, claims data, self-report, face-to-face interview, etc.)				32, 36
8.1.2 Endpoints? (e.g. clinical records, laboratory markers or values, claims data, self-report, patient interview including scales and questionnaires, vital statistics, etc.)				36
8.1.3 Covariates?				33

Section 8: Data sources	Yes	No	N/A	Page Number(s)
8.2 Does the protocol describe the information available from the data source(s) on:				
8.2.1 Exposure? (e.g. date of dispensing, drug quantity, dose, number of days of supply prescription, daily dosage, prescriber)				32,38
8.2.2 Endpoints? (e.g. date of occurrence, multiple event, severity measures related to event)				32-38
8.2.3 Covariates? (e.g. age, sex, clinical and drug use history, co-morbidity, co-medications, life style, etc.)				33
8.3 Is a coding system described for:				
8.3.1 Diseases? (e.g. International Classification of Diseases (ICD)-10)				
8.3.2 Endpoints? (e.g. Medical Dictionary for Regulatory Activities (MedDRA) for adverse events)				
8.3.3 Exposure? (e.g. WHO Drug Dictionary, Anatomical Therapeutic Chemical (ATC)Classification System)				
8.4 Is the linkage method between data sources described? (e.g. based on a unique identifier or other)				37

Comments:

8.3 → No codification system is applied.

Section 9: Study size and power	Yes	No	N/A	Page Number(s)
9.1 Is sample size and/or statistical power calculated?				36

Comments:

9.1 → The number of included patients as well as the duration of the Study is not defined by an official calculation of the sample size as the objective of the observational study is not to confirm or reject any predefined assumptions.

Section 10: Analysis plan	Yes	No	N/A	Page Number(s)
10.1 Does the plan include measurement of excess risks?				
10.2 Is the choice of statistical techniques described?				38
10.3 Are descriptive analyses included?				38
10.4 Are stratified analyses included?				38
10.5 Does the plan describe methods for adjusting for confounding?				
10.6 Does the plan describe methods addressing effect modification?				

Comments:

10.1 → No excess risks are expected due to the design of the non - interventional observational study that aims in describing everyday clinical practice.  
10.5, 10.6 → No methods for adjusting for confounding or addressing effect modification are scheduled due to the fact that no hypothesis testing or assessment of effects is being performed.

Section 11: Data management and quality control	Yes	No	N/A	Page Number(s)

Section 11: Data management and quality control	Yes	No	N/A	Page Number(s)
11.1 Is information provided on the management of missing data?				
11.2 Does the protocol provide information on data storage? (e.g. software and IT environment, database maintenance and anti-fraud protection, archiving)				37
11.3 Are methods of quality assurance described?				40
11.4 Does the protocol describe possible quality issues related to the data source(s)?				40
11.5 Is there a system in place for independent review of study results?				-

Comments:

11.1 → Since this is an observational study where the duration is not defined by an official calculation of the sample size, the objective is to collect data from IPF patients during their participation in the study.  
11.5 → The study design does not require an independent review of the results.

Section 12: Limitations	Yes	No	N/A	Page Number(s)
12.1 Does the protocol discuss: 12.1.1 Selection biases? 12.1.2 Information biases? (e.g. anticipated direction and magnitude of such biases, validation sub-study, use of validation and external data, analytical methods)				39
12.2 Does the protocol discuss study feasibility? (e.g. sample size, anticipated exposure, duration of follow-up in a cohort study, patient recruitment)				36
12.3 Does the protocol address other limitations?				39

Comments:

N/A

Section 13: Ethical issues	Yes	No	N/A	Page Number(s)
13.1 Have requirements of Ethics Committee/Institutional Review Board approval been described?				42
13.2 Has any outcome of an ethical review procedure been addressed?				-
13.3 Have data protection requirements been described?				43

Comments:

N/A

Section 14: Amendments and deviations	Yes	No	N/A	Page Number(s)
14.1 Does the protocol include a section to document future amendments and deviations?				13

Comments:

N/A

Proprietary confidential information © 2018 Boehringer Ingelheim International GmbH or one or more of its affiliated companies

Section 15: Plans for communication of study results	Yes	No	N/A	Page Number(s)
15.1 Are plans described for communicating study results (e.g. to regulatory authorities)?				48
15.2 Are plans described for disseminating study results externally, including publication?				48

Comments:

N/A

### **ANNEX 3. ADDITIONAL INFORMATION**

OUTCOME	DEFINITION
Mortality	

a) Date of death

b) Cause of death

a. Related to IPF

i. Respiratory failure: Is the consequence of lung failure leading to impaired gas exchange; that is, hypoxemia and/or hypercapnia

ii. Acute exacerbation of IPF (see definition below)

iii. Other related to IPF (please specify)

b. Comorbid condition (please specify):

i. Coronary heart disease

ii. Cerebrovascular disease

iii. Pneumonia/respiratory infection (see definition below)

iv. Pulmonary embolism (see definition below)

v. Pulmonary hypertension or Pulmonary arterial hypertension/right heart failure ( see definition below)

vi. Lung cancer (see definition below)

c. Other cause (please specify)

d. Unknown

Acute exacerbation of IPF	

a) Previous or concurrent diagnosis of idiopathic pulmonary fibrosis

b) Unexplained worsening or development of dyspnea within 30 days

c) HRCT with new bilateral ground-glass abnormality and/or consolidation superimposed on a background reticular or honeycomb pattern consistent with usual interstitial pneumonia pattern

d) No evidence of pulmonary infection by endotracheal aspirate or bronchoalveolar lavage

e) Exclusion of alternative causes, including:

a. Left heart failure

b. Pulmonary embolism

c. Identifiable cause of acute lung injury

Myocardial infarction	

a) In patients not undergoing PCI or CABG: A patient has to fulfil either the criteria:

a. Development of significant Q-waves in at least 2 adjacent ECG leads.

 
Or at least 2 of the following three criteria:

OUTCOME	DEFINITION
	
 
b. Typical prolonged severe chest pain of at least 30 min
 
c. ECG changes suggestive of myocardial infarction including ST-changes of T-wave inversion in the ECG).
 
d. Elevation of troponin or CK-MB1 to more than upper level of normal (ULN) or, if CK-MB was elevated at baseline, re-elevation to more than 50% increase above the previous level.
 
b) After PCI (within 24 h) Elevation of troponin or CK-MB1 to more than 3xULN or, if CK-MB is elevated at baseline, re-elevation to more than 3xULN and a more than 50% increase above the previous level, and/or development of significant Q-waves2 in at least two adjacent ECG leads.
 
c) After coronary artery bypass grafting (within 72 h) Elevation of CK-MB1 to more than 5xULN or, if CK-MB was elevated at baseline, re-elevation to more than 5xULN and a more than 50% increase above the previous level, and/or development of significant Q-waves2 in at least two adjacent ECG leads.
 
 
 Total CK if CK-MB was not available  A new Q-wave with a duration of at least 0.04 seconds and a depth of more than a quarter of the amplitude of the corresponding R-wave, in at least 2 adjacent leads

CNS Infarction	
 
a) Ischemic stroke
 
b) Stroke caused by intracerebral hemorrhage
 
c) Stroke caused by subarachnoid hemorrhage
 
d) Stroke caused by cerebral venous thrombosis
 
e) Stroke NOS
 
f) Silent CNS infarction
 
g) Silent cerebral hemorrhage
 

Other Arterial Thromboembolic events (excl. AMI, CNS Infarction, and Pulm embolism)	
 
a) Acute limb ischemia
 
b) Acute mesenteric ischemia
 
c) Renal infarction
 
d) Other (free text)
 

Deep vein thrombosis	
Confirmed by
 
 
- Ultrasound (dd-mm-yy)
 
- Venography (dd-mm-yy)
 
 
and
 
Clinical presentation, i.e. symptomatic/asymptomatic (yes-no-unknown)(such as leg pain, swelling, tenderness of the calf lower extremity) and arm discomfort
 
 
- Edema, dilated venous collateral and discoloration (lower extremity)
 
- no clinical symptoms or signs
 

OUTCOME	DEFINITION
Hemorrhage	
a) Location:
 

a. Gastrointestinal hemorrhage

b. Intracranial hemorrhage

c. Rectal hemorrhage

d. Epistaxis

e. Hemorrhage NOS

 
b) Severity:
 

a. Major bleeding, defined as meeting one or more of the following criteria):

i. Overt bleeding associated with a reduction in hemoglobin of at least 20 grams per liter or leading to a transfusion of at least 2 units of blood or packed cells

ii. Symptomatic bleeding in a critical area or organ: Intraocular, intracranial, intraspinal or intramuscular with compartment syndrome, retroperitoneal bleeding, intra-articular bleeding or pericardial bleeding

iii. Life-threatening bleeding

iv. Fatal bleeding

b. Life-threatening bleeding, as defined as meeting one or more of the following criteria:

i. Symptomatic intracranial bleed

ii. Reduction in hemoglobin of at least 50 grams per liter

iii. Transfusion of at least 4 units of blood or packed cells, associated with hypotension requiring the use of intravenous inotropic agents

iv. Necessitated surgical intervention

v. Fatal bleeding

 
c) Circumstances:
 

c. peri/postoperative

d. accident/ injury

e. other (please specify)

f. unknown

Gastrointestinal perforation	

a) Perforation of gastric ulcer

b) Perforation of duodenal ulcer

c) Perforation of small-intestine diverticulum

d) Perforation of colon diverticulum

e) Peritonitis as a complication of appendicitis

f) Perforation as procedural complication (endoscopy),

Proprietary confidential information © 2018 Boehringer Ingelheim International GmbH or one or more of its affiliated companies

OUTCOME	DEFINITION
	g) Others (please specify)
Pulmonary hypertension	a) Right-heart catheterization performed (mPAP>25 mmHg at rest) b) No RHC performed / Diagnosed by echocardiography or clinical diagnosis
Hospitalizations	a) Date entry b) Date discharge c) Hospitalization that requires mechanical ventilation (Yes/No) d) Hospitalization that includes ICU (Yes/No) e) Hospitalization due to respiratory cause (Yes/No) If Yes: a. Due to Acute exacerbation b. Due to IPF worsening other than Acute Exacerbation c. Other respiratory causes, NOS (e.g. pneumonia, pneumothorax,...) – please specify

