### **9.8.1 Main Analysis**

The objective of this registry is neither to confirm nor to reject any predefined hypothesis; therefore the nature of the statistical analyses will be exploratory and descriptive.

Continuous variables will be listed as median with interquartile and other percentages, and as mean value with standard deviation (SD), along with minimum and maximum values (depending on the underlying distribution). Categorical values will be listed as absolute and relative frequencies. All events during follow up will be described as incidence rates with 95% confidence interval (CI).

Stratified analyses will be performed among newly diagnosed patients (< 6 months) as well as patients that were diagnosed in the past ( $\geq 6$  months). In case of conflicting results those of the newly diagnosed will be the decisive. Due to limited number of patients and population heterogeneity, no comparison between treatments can be done and no causal relationship conclusion can be derived (no hypothesis testing). Statistical analyses will be performed with IBM SPSS Statistics (Version 19.0).

If it was not avoidable to select patients from sites with other ongoing registries, patients enrolled in other registries in parallel need to be analyzed separately. In case of difference the results for the BI registry patients are decisive.

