**7.8 SAFETY ANALYSIS****7.8.1 Adverse events**

Safety analysis will be performed in the FAS population. No stratified analysis for safety will be considered. All adverse events will be coded according to MedDRA dictionary.

The analyses of adverse events (AEs) will be descriptive in nature. All analyses of AEs will be based on the number of subjects with AEs and NOT on the number of AEs.

The frequency of subjects with adverse events following the ICF signature will be summarized according to primary system organ class and preferred term (MedDRA version to be displayed in the tables). System organ classes will be sorted alphabetically, preferred terms will be sorted by frequency (within system organ class).

Summary statistics will be provided for the following categories: all AEs, all SAEs and AEs with causal relationship to BI medication. AE listings will also be provided.

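### The re-elevation condition in the myocardial infarction definition covers CK-MB but not troponin, so a persisting troponin can be classified as a new infarction

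*Protocol*

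**What the plan says.** Protocol Annex 3 gives three routes to a myocardial infarction.

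- **a) No procedure.** This route is headed for patients **not** "undergoing PCI or CABG: A patient has to fulfil either the criteria". It needs either significant Q-waves or two of three items: prolonged chest pain (item b), ECG changes (item c) and marker elevation (item d). Item d accepts troponin or CK-MB above the ULN. Its clause for a marker already raised reads "if CK-MB was elevated at baseline, re-elevation to more than 50% increase above the previous level".
- **b) After PCI.** "After PCI (within 24 h) Elevation of troponin or CK-MB" is the marker test, with the threshold and clause "to more than 3xULN or, if CK-MB is elevated at baseline, re-elevation to more than 3xULN and a more than 50% increase", where the rise is measured against the preceding value. Development of significant Q-waves also qualifies.
- **c) After CABG.** "After coronary artery bypass grafting (within 72 h) Elevation of CK-MB" is the marker test, with a 5xULN threshold and a matching CK-MB clause. Troponin is not used.

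A footnote lets total CK stand in where CK-MB is not available.

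On analysis, protocol section 9.8.1 says: "All events during follow up will be described as incidence rates with 95% confidence interval (CI". It does not say whether first or all events are counted. SAP section 7.8.1 says: "All analyses of AEs will be based on the number of subjects with AEs and NOT on the number of AEs". That sentence is about adverse events; the SAP gives no counting rule for the Annex 3 outcomes. Neither document describes adjudication of events.

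**The concern.** In a)d and b) either marker can establish the event, but the test for a further rise depends on CK-MB alone. The CABG route shows the contrast: one marker, and the clause matches it. Annex 3 also asks for novelty elsewhere, for example in the Q-wave footnote and in the HRCT item for acute exacerbation. The omission for troponin therefore looks like a drafting gap and not a deliberate choice.

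Protocol section 8 names infarction among the conditions on which the registry will report. If residual or chronically raised troponin can satisfy the definition, the reported infarction frequency mixes new events with carry-over from old ones. The written definition is the only filter.

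**Working it through.** The plan has no figure to reproduce here. The check is a reading of the text, a logic test and an illustration of size.

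**1. Logic test of b).** Markers are in multiples of ULN, pre-PCI → within 24 h after PCI, with no new Q-wave. All values are illustrative assumptions. Four readings:

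- R1: the alternatives are taken literally, any one sufficing.
- R2: the re-elevation clause replaces the CK-MB limb only.
- R3: if CK-MB is raised at baseline, the clause replaces the whole marker test.
- R4: as R2, but troponin must newly cross 3xULN.

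| Pattern | R1 | R2 | R3 | R4 |
|---|---|---|---|---|
| Troponin 20→18, CK-MB 0.8→0.9 | met | met | met | not met |
| Troponin 20→18, CK-MB 6→5 | met | met | not met | not met |
| Troponin 20→18, CK-MB 2→2.2 | met | met | not met | not met |
| Troponin 2→2.5, CK-MB 0.8→0.9 | not met | not met | not met | not met |
| Troponin 2→2.5, CK-MB 2→2.5 | not met | not met | not met | not met |

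With CK-MB normal, a falling troponin above 3xULN meets b) unless a new troponin rise is required. If only troponin is measured, the CK-MB clause cannot be triggered at all. That is plausible, because the protocol requests no tests beyond routine practice.

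**2. Grid.** Levels 0.5, 2, 4, 10 and 20; troponin raised before PCI; neither marker rising. Troponin pairs: 2+3+4+5 = 14. CK-MB pairs: 1+2+3+4+5 = 15. Total 14 × 15 = 210. Post-PCI troponin exceeds 3 in 1+2+3 = 6 of the 14 pairs, and post-PCI CK-MB exceeds 3 in 6 of the 15.

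- R1: 210 − (8 × 9) = 138 meet b).
- R2: 6 × 15 = 90.
- R3: 6 × 1 = 6 (only the pair with normal CK-MB at baseline).
- R4: 0.

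These are counts of assumed patterns, not proportions of patients. They show that the result depends on the reading.

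**3. What a classification under b) does to the count.**

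| Situation | Effect |
|---|---|
| Index infarction before PCI; a) covers it; all events counted | second count possible |
| Same; first events only | one count, no inflation |
| Index infarction before PCI; a) excludes anyone who has PCI | one count, reached only through the gap |
| No infarction; stable troponin above 3xULN; PCI | false first event under any counting rule |
| No procedure; chronically raised troponin plus one other item of a) | item d met without a rise |

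The documents do not settle the scope of a) or first versus all events.

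**4. Size, by assumption only.** Take 300 patients (protocol section 9.6), assumed mean follow-up of 1.6 years, so 300 × 1.6 = 480 person-years, and 8 assumed true infarctions. The rate is 8/480 = 1.67 per 100 person-years (exact Poisson 95% CI 0.72 to 3.28). If a share s of these is counted twice, events become 8(1 + s), so the inflation equals s.

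- s = 0: 1.67, inflation 0%.
- s = 0.5: 12/480 = 2.50 (1.29 to 4.37), inflation 50%.

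The percentage only returns the share put in.

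**The case against.** A reader might infer that every infarction treated by PCI automatically meets b) and is counted again, so that the rate is biased upward by the share treated with PCI. The documents do not support this, for four reasons.

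- Troponin must exceed 3xULN within the 24 h window, and under R3 the 50% test applies when CK-MB is also raised.
- Route a) is headed for patients without PCI or CABG. Read literally, a PCI-treated patient is assessed under b) only and counted once.
- No document says that repeat infarctions are counted. The SAP plans frequencies (section 7) and counts adverse events by subject.
- The direction is not established as upward only. Under R3 the present text may already miss a patient whose raised CK-MB does not rise further.

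All four stand. They remove the automatic double count and any stated inflation, but not the gap. If a) excludes anyone who has PCI, an infarction that came before the procedure qualifies only because residual troponin, or a CK-MB value, happens to meet b). And a false first event from stable troponin survives subject-level counting.

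It can also be argued that elevation to a level already implies a rise. That is a possible reading (R4), but Annex 3 adds a separate clause for CK-MB already raised and so does not rely on that word alone.

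The chronic-troponin case under a) is weaker. It needs a second item, and calling a fixed old ECG abnormality a change is an uncharitable reading. The documents give no frequency for it.

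**Conclusion.** The gap is real. The re-elevation condition in a)d and b) names CK-MB only, so a troponin raised before PCI and still above 3xULN within 24 h can be classified as a post-PCI infarction with no further rise. Item a)d has the same gap for chronically raised troponin. This holds where CK-MB is normal or unmeasured on every reading except one that requires a new troponin rise; where CK-MB is also raised, it depends on the reading.

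The effect on the reported rate cannot be derived from the documents. It may be a second count, a false first event, or the only count of the index infarction, and the possible inflation starts at 0%. This is a descriptive registry with no hypothesis tests, so the consequence is limited to the infarction figures. With few infarctions, however, a handful of misclassified cases would be visible.

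**What to change.** Make three changes together.

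1. **Annex 3, a)d and b).** Apply the existing re-elevation condition to whichever marker is used, troponin or CK-MB. No new threshold is proposed.
2. **Annex 3, heading of a).** State that a) covers infarctions occurring before a procedure, and reconcile it with b). Without this, change 1 could leave a PCI-treated infarction with falling markers and no new Q-wave meeting neither route. In the illustration above, with half of the 8 infarctions treated by PCI and all of these lost, 8 − 4 = 4 events remain, or 4/480 = 0.83 per 100 person-years.
3. **SAP.** Count a post-PCI event as a separate infarction only if it meets the re-elevation condition relative to the pre-procedure value, and state whether infarction rates use first or all events. Name that reference value explicitly, because SAP section 6.7 defines baseline as the first measurement after enrolment.

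Adding the word new to the ECG item in a) would be a clarification only.

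The cost is a few words in each document and a re-check of the infarctions already recorded. A pre-procedure marker value must be looked up where it exists; it may be missing for some patients.
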